**Table 4 Study Treatment Dose Reduction and Interruption Instructions**

Treatment-Related Toxicity a,b including hepatic injury and thromboembolic events	Management	Dose Adjustment

Grade 1 or Tolerable Grade 2		
	Continue treatment	No change (continue at Level 0)
Intolerable Grade 2c,d or Grade 3		
First occurrence	Interrupt until resolved to Grade 0-1 or baseline	Dose level -1 once a day (20 or 14 mg QD) (1-level reduction from previous)
Second occurrence (same toxicity or new toxicity)	Interrupt until resolved to Grade 0-1 or baseline	Dose level -2 once a day (14 or 10 mg QD) (1-level reduction from previous)
Third occurrence (same toxicity or new toxicity)	Interrupt until resolved to Grade 0-1 or baseline	Dose level -3 once a day (10 or 8 mg QD) (1-level reduction from previous)
Fourth occurrence (same toxicity or new toxicity)	Interrupt until resolved to Grade 0-1 or baseline	Stop Treatment or discuss possible dose level -4 with sponsor (8 or 4 mg QD) (1-level reduction from previous)
Grade 4e: Discontinue Study Treatment		

Note: For grading see Common Terminology Criteria for Adverse Events version 4.03. Collect all grades of adverse events, decreasing and increasing grade.

QD = once daily.

- a: A delay of study treatment for more than 28 days (due to treatment-related toxicities) will require a discussion with the sponsor before treatment can be resumed.
- b: Initiate optimal medical management for nausea, vomiting, and/or diarrhea prior to any study treatment, interruption, or dose reduction.
- c: Applicable only to Grade 2 toxicities judged by the subject and/or physician to be intolerable.
- d: Obese subjects with weight loss do not need to return to baseline weight or Grade 1 weight loss to restart lenvatinib. There should be no weight loss for at least 1 week, and subjects should be started at the lower dose. Normal body mass index should be used as a reference for future dose reductions.
- e: Excluding laboratory abnormalities judged to be non-life-threatening, in which case manage as Grade 3.

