#### 9.5.1.4 Safety Assessments

The rate of TEAEs with CTCAE grades of 3 or higher within 24 weeks after randomization (as of the Week 24 time point) is a primary study endpoint. Determination of the overall safety profile and tolerability of lenvatinib, the time to treatment discontinuation due to an AE, number of dose reductions, and the time to first dose reduction are secondary study endpoints. As part of the overall safety and tolerability assessment, the rate of TEAEs of Grade 2 that are intolerable and lead to dose reduction, dose interruption, or drug discontinuation will be determined (Section 7.2).

Safety assessments will consist of monitoring and recording all AEs, including all CTCAE v4.03 grades (for increasing severity), and SAEs; regular laboratory evaluation for hematology, blood chemistry, and urine values, periodic measurement of vital signs, ECGs; and the performance of physical examinations as detailed in Table 7. An ECG or multiple-gated acquisition (MUGA) scan including left ventricular ejection fraction (LVEF) will be performed at screening and as clinically indicated.

A pregnancy test will be administered to women of childbearing potential at the Screening Visit, Baseline Visit, at the beginning of Cycles 2 and 3, and at the time the subject is off-study.

Progression of a subject's thyroid cancer and signs and symptoms clearly related to disease progression should not be captured as an AE. Disease progression is a study endpoint and should be captured in the CRF as per the guidelines for reporting disease progression.

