##### 9.7.1.8.1 PRIMARY SAFETY ENDPOINT

For the analysis of the primary safety endpoint, the frequency (number and percentage) of TEAEs with CTCAE grade of 3 or higher will be summarized by treatment group (24 mg and 18 mg); the difference in the frequency between the 2 treatment groups will be presented with 95% CI.

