### 9.7.1.8.3 ADVERSE EVENTS

The AE verbatim descriptions (investigator terms from the CRF) will be classified into standardized medical terminology using the Medical Dictionary for Regulatory Activities (MedDRA). Adverse events will be coded to the MedDRA (Version 16.1 or higher) lower level term closest to the verbatim term. The linked MedDRA preferred term and primary system organ class (SOC) are also captured in the database.

TEAEs will be defined as AEs that emerge during treatment, having been absent pretreatment (at baseline) or those that:

- Reemerges during treatment, having been present at pretreatment (Baseline) but stopped before treatment, or
- Worsens in severity during treatment relative to the pretreatment state, when the AE is continuous.

Only those AEs that are treatment-emergent will be included in summary tables. All AEs, treatment-emergent or otherwise, will be presented in subject data listings.

An overview table, including the incidence of and the number of subjects with TEAEs, SAEs, deaths, and those TEAEs that led to study drug discontinuation, dose modification, or dose interruption will be provided.

The incidence of TEAEs will be summarized by SOC, preferred term, CTCAE grade, and relatedness to study drug. All summaries will be performed by treatment group. Although a MedDRA term may be reported more than once for a subject, that subject will be counted only one time in the incidence count for that MedDRA term with the highest CTCAE grade (in the summary by CTCAE grade) or with the closest relationship to study treatment (in the summary by relatedness to study treatment).

The number (percentage) of subjects with TEAEs will also be summarized by relationship to study drug (Yes [related] and No [not related]).

In addition, the overall proportion of subjects with TEAEs of CTCAE Grade 3 or higher and the overall proportion of subjects with intolerable CTCAE Grade 2 TEAEs that result in dose modification will be analyzed using the same approach for the primary safety endpoint, as sensitivity analyses.

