5.6 Safety Analyses

All safety analyses will be performed on the Safety Analysis Set. Safety data, presented by the starting lenvatinib dose of 24 mg or 18 mg and overall will be summarized on an “as treated” basis using descriptive statistics (i.e., n, mean, standard deviation, median, minimum, and maximum values for continuous variables; n [%] for categorical variables). Safety variables include TEAEs, TEAEs with CTCAE Grade ≥ 3 , intolerable TEAEs of CTCAE Grade 2 (based on data collected in CRF), treatment-related TEAEs, treatment-emergent serious adverse events (SAEs), clinical laboratory parameters, vital signs, 12-lead ECG results, ECOG PS scores, and left ventricular ejection fraction (LVEF). Abnormal values will be flagged.

Study Day 1 for all safety analyses is defined as the date of the first dose of study drug.

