5.6.2 Adverse Events

The AE verbatim descriptions (investigator terms from the CRF) will be classified into standardized medical terminology using the MedDRA. Adverse events will be coded to MedDRA (version 23.0) lower level term (LLT) closest to the verbatim term. The linked

MedDRA PT and primary SOC will also be captured in the database. The CTCAE grading (version 4.03) will be included in the database.

A TEAE is defined as an AE that emerged during treatment (from time of first dose up to 28 days following the last dose of study drug), having been absent pretreatment (Baseline) or

- Reemerged during treatment, having been present pretreatment (Baseline) but stopped before treatment, or
- Worsened in severity during treatment relative to the pretreatment state, when the AE was continuous

Only TEAEs will be summarized. A subject will be counted only once within each category (i.e., SOC, PT, worst grade, or other specific category to be summarized in table) even if the subject experienced more than 1 TEAE within the category. All AEs, treatment-emergent or otherwise, will be presented in subject data listings.

For the analysis of the primary safety endpoint of rate of TEAEs with CTCAE Grade ≥ 3 within 24 weeks after randomization (as of the Week 24 time point), the number (percentage) of subjects with TEAEs of CTCAE Grade ≥ 3 as of Week 24 will be reported; the difference in frequency between the treatments (18 mg minus 24 mg) will be presented with 95% CI, using asymptotic normal approximation. In addition, the number (percentage) of subjects with TEAEs with CTCAE Grade ≥ 3 as of the Week 24 will be summarized by SOC and PT.

The incidence of TEAEs will be reported as the number (percentage) of subjects with TEAEs by SOC, PT and worst CTCAE grade. The number (percentage) of subjects with TEAEs will also be summarized by PT and worst CTCAE grade.

The number (percentage) of subjects with treatment-related TEAEs, TEAEs leading to treatment discontinuation, TEAEs leading to dose reduction/interruption, will be summarized by SOC, PT and worst CTCAE grade. All SAEs, treatment-related SAEs, fatal TEAEs, and nonfatal SAEs will be summarized by SOC and PT. Treatment-related TEAEs include those events considered by the investigator to be related to study treatment or TEAEs with a missing causality on the CRF.

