7 CHANGES IN THE PLANNED ANALYSES

This SAP focuses on the analyses for the 2-arm design of the study.

The Safety Analysis Set will be used for the summary table of biomarker parameters, while the Pharmacodynamic Analysis Set will be defined in a separate SAP for PK/PD analyses.

The exploratory endpoint of Duration of Clinical Benefit will not be analyzed in this study as it is not a widely used and well-defined endpoint; furthermore, it was not included in the RR-DTC Phase 3 study, E7080-G000-303.

Clinically abnormal ECG results based on QTcB and QTcF will be summarized the same way as done in Study E7080-G000-303. The categories are slightly different than the ones stated in the study protocol.

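### SAP 5.6.2 omits, without declaring it, the between-arm difference and 95% CI that protocol 9.7.1.8.3 requires for overall Grade 3 or higher TEAEs and for dose-modifying intolerable Grade 2 TEAEs

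*SAP*

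**What the plan says.** **Protocol.** Section 9.7.1.8.1 analyses the primary safety endpoint by number and percentage per arm, and adds that "the difference in the frequency between the 2 treatment groups will be presented with 95% CI". Section 9.7.1.8.3 extends that method, as sensitivity analyses, to the overall proportion with Grade 3 or higher TEAEs and to a second proportion: "overall proportion of subjects with intolerable CTCAE Grade 2 TEAEs that result in dose modification will be analyzed using the same approach". Section 9.5.1.4 states that "the rate of TEAEs of Grade 2 that are intolerable and lead to dose reduction, dose interruption, or drug discontinuation will be determined". The synopsis (Safety Analyses) is weaker and asks only for a descriptive summary of intolerable Grade 2 TEAEs.

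**SAP.** Section 5.6.2 gives a between-arm difference with 95% CI for one safety quantity, Grade 3 or higher TEAEs as of Week 24: "the difference in frequency between the treatments (18 mg minus 24 mg) will be presented with 95% CI, using asymptotic normal approximation". Section 5.6 keeps "intolerable TEAEs of CTCAE Grade 2 (based on data collected in CRF" among the safety variables, summarised descriptively by starting dose. Section 5.6.2 also tabulates TEAEs leading to discontinuation, and those leading to dose reduction or interruption, by worst grade. It provides a listing of AEs of intolerable Grade 2 or above. Section 5.6.1 reports dose modifications and Kaplan-Meier quartiles for time to first dose reduction.

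Section 7, on changes from the protocol, opens with "This SAP focuses on the analyses for the 2-arm design of the study". It then covers the analysis set for biomarkers, duration of clinical benefit and the QTc categories. It says nothing about the safety sensitivity analyses.

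**The concern.** The primary objective asks whether 18 mg has an improved safety profile. The primary safety endpoint has no test, margin or success rule, so the answer will be read from a difference and its interval.

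The endpoint counts Grade 3 or higher only. Protocol Table 4 puts Grade 3 and intolerable Grade 2 toxicity in the same row of consequences, with the qualifier "Applicable only to Grade 2 toxicities judged by the subject and/or physician to be intolerable". If the lower start turns some Grade 3 events into Grade 2 events that still lead to a dose change, the primary safety endpoint falls while the burden of dose-changing toxicity may not. The protocol's second sensitivity analysis would put an estimate and interval on the other side of that exchange. The first would show whether the 24-week contrast persists over the whole treatment period. The SAP as written produces neither, and nothing tells its reader that they were planned.

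**Working it through.** **1. The two documents side by side**

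| Quantity | Protocol 9.7.1.8.1 and 9.7.1.8.3 | SAP 5.6 to 5.6.2 |
|---|---|---|
| Grade 3+ as of Week 24 | n (%), difference, 95% CI | n (%), difference, 95% CI |
| Grade 3+, overall | same approach | n (%) only |
| Intolerable Grade 2 with dose modification, overall | same approach | descriptive variable and listing; dose-changing TEAEs by worst grade |
| Declared in SAP Section 7 | not applicable | no |

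Two observations suggest oversight rather than a decision. SAP 5.4.1 carries over the efficacy sensitivity analysis (overall ORR), and Section 7 reports even a small change in QTc categories. Version timing does not explain the gap either. The SAP is written to Amendment 05, and the amendment log entries for 05 and 06 do not mention these analyses.

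**2. The plan's own precision figure**

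Inputs from protocol 9.7.2: 76 per arm, a Grade 3+ rate of 70.5% at 24 mg, and a stated half-width of about 15 points.

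Half-width = 1.96 × √[p₁(1−p₁)/76 + p₂(1−p₂)/76]

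- 70.5% in both arms: 1.96 × √(2 × 0.705 × 0.295/76) = 14.5 points.
- 70.5% against 60.5%: 15.0 points. Against 50%: 15.2 points.

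The stated figure reproduces.

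**3. Precision of the omitted Grade 2 comparison**

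The documents give no rate for intolerable Grade 2 TEAEs, so the rates here are assumptions. With equal rates of 20% the half-width is 1.96 × √(2 × 0.20 × 0.80/76) = 12.7 points. With 40% it is 15.6 points. This is similar to the precision accepted for the primary safety endpoint.

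**4. Illustration of a grade shift (assumed)**

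Suppose a given percentage of 18 mg subjects move from Grade 3+ to a dose-modifying intolerable Grade 2 event that they would not otherwise have had. Take both proportions over the same period, with 70.5% Grade 3+ at 24 mg. Differences are 18 mg minus 24 mg, in points, with 95% CI.

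| Shift | Grade 3+ | Grade 2, 24 mg rate 5% | Grade 2, 24 mg rate 20% |
|---|---|---|---|
| 10 | -10.0 (-25.0 to +5.0) | +10.0 (+0.6 to +19.4) | +10.0 (-3.7 to +23.7) |
| 15 | -15.0 (-30.2 to +0.2) | +15.0 (+4.8 to +25.2) | +15.0 (+1.0 to +29.0) |
| 20 | -20.0 (-35.2 to -4.8) | +20.0 (+9.1 to +30.9) | +20.0 (+5.8 to +34.2) |

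For the 15-point row, the Grade 3+ half-width is 1.96 × √[(0.705 × 0.295 + 0.555 × 0.445)/76] = 15.2. The Grade 2 half-width at the 5% rate is 1.96 × √[(0.05 × 0.95 + 0.20 × 0.80)/76] = 10.2.

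The table is a best case for detecting the exchange. The protocol analysis counts any subject with a qualifying Grade 2 event, including those who also had Grade 3, and I read its word overall as the whole treatment period. Subjects who would have had such a Grade 2 event anyway add nothing to the difference, so the real rise could be smaller than the fall in Grade 3+.

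**The case against.** A reader might infer that the SAP drops intolerable Grade 2 toxicity altogether, so that a shift in grade would pass as better safety. The documents do not support that. Per-arm rates of intolerable Grade 2 TEAEs, dose-changing TEAEs by worst grade, frequency of dose modification, and time to first dose reduction and to discontinuation due to an AE all stay in the SAP. If dose-limiting toxicity were unchanged at 18 mg, these outputs could show it.

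A reader might also infer that the protocol added the Grade 2 analysis in order to catch a grade shift. It calls the analysis a sensitivity analysis and gives no such reason. Nor are the consequences of Grade 3 and intolerable Grade 2 identical throughout. Table 4 covers treatment-related toxicity, and hypertension has its own pathway in protocol 9.4.2.1.

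The synopsis supports the SAP's descriptive approach, and 9.5.1.4 asks only for a rate. With n (%) per arm, anyone can compute a difference and interval afterwards. No decision rule depends on it.

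All of this stands and limits the point, but it does not remove it. Section 9.7.1.8.3 is the specific analysis section and it names the method. The Grade 2 proportion also cannot be rebuilt reliably from the dose-change tables. Discontinuations are tabulated separately from reductions and interruptions, and a subject counted at worst grade in an overall row disappears from Grade 2 once a Grade 3 event occurs. SAP 5.6 does not tie its intolerable Grade 2 variable to dose modification, although the CRF confirmation in protocol 9.5.1.4.1 does. A difference computed after unblinding is not the prespecified one.

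**Conclusion.** The point holds as an undeclared omission of two protocol-required comparisons, with the descriptive data retained. It changes no sample size and no primary analysis. What is lost is the prespecified estimate and 95% CI for two quantities that bear on the safety half of the primary objective. On the primary safety endpoint alone, a move from Grade 3 to dose-modifying Grade 2 counts in full as improvement.

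The discrepancy itself rests on the text and needs no assumption. Its possible size does. With assumed 24 mg rates of 5% to 20%, the omitted comparison would have a 95% CI above zero for a 15- or 20-point shift. For a 10-point shift it would be above zero at the 5% rate but not at 20%. The documents give no evidence that such a shift will occur.

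**What to change.** - In SAP 5.6.2, add the number (%), the difference (18 mg minus 24 mg) and the 95% CI by normal approximation for (a) Grade 3 or higher TEAEs and (b) intolerable Grade 2 TEAEs resulting in dose modification, both over the whole treatment period and labelled as sensitivity analyses. Alternatively, declare and justify the omission in SAP Section 7.
- State what dose modification means in (b). Protocol 9.5.1.4 lists reduction, interruption and discontinuation, SAP 5.6.1 lists reduction and interruption, and the overview table in protocol 9.7.1.8.3 names modification apart from the other two.
- Reconcile the descriptive-only wording of the protocol synopsis with 9.7.1.8.3.
- Optionally, add the composite of Grade 3 or higher or dose-modifying intolerable Grade 2 as of Week 24. Neither document requires it.

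The cost is a few lines of SAP text and one or two tables. No new data are needed, because the CRF already records the investigator's confirmation that a dose-changing Grade 2 event was intolerable (protocol 9.5.1.4.1). The change should be made before unblinding.

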#### **Duration of Treatment**

The duration of treatment for each subject is estimated to be:

*Prerandomization Phase:* 4 weeks

*Randomization Phase:* Depending upon when a subject is enrolled, their time on treatment may range from 6 months to 42 months. Treatment will continue until disease progression, development of unacceptable toxicity, subject request to discontinue, withdrawal of consent, subject is lost to follow-up, sponsor termination of the study, or until the **End of Study**. Subjects still on treatment will remain on blinded investigational product until the primary analysis is complete and will continue to receive investigational product until they complete the Off-treatment visit prior to their transition to commercial lenvatinib or an access program. While receiving investigational product, subjects should continue with the same assessments as noted in the Schedule of Assessments and Procedures.

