5.6.1 Extent of Exposure

Treatment period consisted of 28-day blinded study treatment cycles (i.e., 1 to 28 days per cycle) (Section 3.2). Per protocol, subjects received 1 of the 2 starting doses, lenvatinib 24 mg/day or lenvatinib 18 mg/day. Dose reductions would occur in succession based on the subject's previous dose level (24, 20, 14, 10, and 8 mg QD, or 18, 14, 10, 8, and 4 mg QD, respectively).

The following analyses will be performed:

- Duration of Treatment (months): $(\text{last dose date} - \text{first dose date} + 1) / (365.25/12)$
- Number of Subject-months: sum of treatment time (in months) for all subjects (including dose interruption).
- Total dose (mg) taken per subject
- Dose intensity (mg/day) per subject (i.e., total dose/treatment duration), relative dose intensity (%) per subject (i.e., percentage of dose intensity relative to the planned dose at Baseline)
- Dose modification (reduction, interruption), frequency of dose modification
- Treatment discontinuation due to AE (from treatment disposition page)
- Time to first dose reduction (weeks), time to treatment discontinuation due to AE (weeks). Both will be analyzed using KM method (same as for PFS, see Section 5.4.1) and estimated quartiles and the 95% CI will be presented.

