In addition, summaries of clinically significant TEAEs (CSEs) (i.e., subject incidence, time to first onset of Grade 3 or 4) will be provided. [Appendix 13.2](#) includes the list of CSEs. These CSEs include those AEs known to be of concern with lenvatinib or of VEGF-targeted agents in general.

TEAEs, SAEs, treatment-related TEAEs, treatment-related SAEs, CSEs will also be summarized by PT in decreasing frequency.

The number (percentage) of subjects with all deaths and deaths on treatment or within 30 days of last lenvatinib dose will be summarized.

Subject data listings for (1) all AEs, (2) AEs of CTCAE Grade 2 (intolerable) or above, (3) serious adverse events, (4) fatal AEs, (5) all deaths, (6) AEs leading to treatment discontinuation, and (7) AEs leading to dose reduction or interruption will be provided.

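### Whole-study TEAE, SAE and CSE incidence is a crude percentage over treatment time that may differ between arms, so it can hide or exaggerate a safety difference; the Week 24 primary safety result is not affected

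*SAP*

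**What the plan says.** SAP 5.6.2 defines a TEAE by a window running "from time of first dose up to 28 days following the last dose of study drug". Within that window "A subject will be counted only once within each category", and the general rule is that "The incidence of TEAEs will be reported as the number (percentage) of subjects with TEAEs by SOC, PT and worst CTCAE grade". Treatment-related TEAEs and TEAEs leading to discontinuation or dose change are also given as numbers and percentages. For serious events, "All SAEs, treatment-related SAEs, fatal TEAEs, and nonfatal SAEs will be summarized by SOC and PT". For the events of special concern, "summaries of clinically significant TEAEs (CSEs) (i.e., subject incidence, time to first onset of Grade 3 or 4) will be provided".

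The protocol adds a whole-study comparison between arms. Section 9.7.1.8.3 names the overall proportion with Grade 3 or higher TEAEs as a sensitivity analysis, using the method of the primary safety endpoint, which is a difference with a 95% CI.

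On exposure, the protocol synopsis (Duration of Treatment) says: "Depending upon when a subject is enrolled, their time on treatment may range from 6 months to 42 months". Treatment can end earlier for progression, toxicity or other reasons. SAP 5.6.1 sums treatment time into subject-months, but as an exposure statistic only.

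Two analyses in SAP 5.6.2 have a fixed window: the primary safety endpoint (Grade 3 or higher within 24 weeks of randomization) and the Grade 3 or higher table by SOC and PT as of Week 24. SAP 5.6.1 plans Kaplan-Meier summaries of time to first dose reduction and time to discontinuation for an AE.

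**The concern.** A crude percentage depends on two things: how often events happen per month, and how many months subjects are watched. In these tables the second depends on the dose. A better tolerated dose may be taken longer; a less effective one may be stopped sooner for progression.

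The sponsor's own simulations point both ways. Protocol Table 2 has 68.5% of subjects with at least one dose reduction by 24 weeks on 24 mg and 57.3% on 18 mg. Table 1 has response rates of 50.0% and 41.5%. Much of the exposure may also fall after Week 24: median PFS on lenvatinib in Study 303 was 18.3 months (protocol 7.1).

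Overall safety profile and tolerability is a secondary endpoint. SAEs, fatal TEAEs and CSE incidence have no fixed-window table. A real advantage of 18 mg could disappear from these tables, or a shorter-treated 18 mg arm could look safer than it is.

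**Working it through.** **The plan's own safety figure.** SAP Section 4 states a 95% CI half-width of about 15% for the primary safety difference. The formula is 1.96 × √[(p₁(1−p₁) + p₂(1−p₂))/76], with p₁ = 0.705 for 24 mg. If p₂ is 0.705, 0.60 or 0.50, the half-width is 14.5, 15.0 or 15.2 points. The figure reproduces. What follows concerns an analysis that is absent, not a wrong number.

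**Inputs for the illustration.** From the documents: a 28-day post-dose window, or 28/30.4375 = 0.92 months; possible treatment time of 6 to 42 months; 76 subjects per arm. Assumed, because the documents give no values by arm: exponential treatment time T with medians of 12 and 18 months; data cutoff C uniform from 5.5 to 41.5 months after first dose (24 weeks plus 36 months of accrual); event hazard h(t) independent of stopping.

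**Formulas.** A subject is at risk until the first event, T + 0.92, or C, whichever is earliest. Write S(t) = exp(−∫₀ᵗ h), and A(t) = P(T + 0.92 > t) × P(C > t).
- Crude incidence = ∫ h(t) S(t) A(t) dt
- Time at risk per subject = ∫ S(t) A(t) dt
- Exposure-adjusted rate = crude incidence ÷ time at risk

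**Constant hazard.** The arm with the 12-month median comes first.

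| Monthly hazard, 12-month arm | Crude, equal hazards | Gap (points) | Crude, hazard 20% lower on 18-month arm | Gap (points) |
|---|---|---|---|---|
| 0.02 | 21.1% vs 24.7% | +3.5 | 21.1% vs 20.5% | −0.6 |
| 0.04 | 36.1% vs 41.3% | +5.2 | 36.1% vs 35.4% | −0.7 |
| 0.08 | 55.3% vs 61.4% | +6.1 | 55.3% vs 54.9% | −0.4 |

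Gaps are taken before rounding. The exposure-adjusted rate recovers the truth here: a ratio of 1.00 in the equal-hazard column and 0.80 in the other.

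**Opposite direction.** With equal hazards of 0.04 and medians of 14 and 11 months, crude incidence is 38.2% and 34.9%. The shorter-treated arm looks 3.3 points safer with no true difference.

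**When the benefit cancels.** Without a cutoff or post-dose window, the crude proportion is λ/(λ + 1/τ) for hazard λ and mean duration τ. Two arms match when the ratio of durations equals 1 ÷ the hazard ratio. For a hazard ratio of 0.80 that is 1.25.

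**Front-loaded hazard.** The documents suggest early toxicity: 70.5% with Grade 3 or higher by 24 weeks (SAP Section 4) and a median of 3 months to dose reduction in Study 303 (protocol 7.1). Assume 0.10 per month for 3 months, then 0.01, identical in both arms, with medians of 12 and 18 months.
- Crude incidence: 31.6% vs 33.5%, a false gap of about 2 points (ratio 1.06).
- Exposure-adjusted rate: 3.46 vs 3.12 per 100 subject-months, ratio 0.90. This is a false 10% advantage for the longer-treated arm.

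**Fixed-time cumulative incidence, 1 − S(t).** In the front-loaded case both arms have 1 − exp(−(0.30 + 0.01 × 9)) = 32.3% at 12 months, so no false difference appears. With constant hazards of 0.04 and 0.032 the 12-month values are 38.1% and 31.9%, in the right direction.

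**The case against.** The strongest reply is that the trial's safety question is already protected. The primary objective ties improved safety to Grade 3 or higher TEAEs in the first 24 weeks, and that endpoint and its SOC and PT table have a fixed window. Tolerability has Kaplan-Meier analyses, CSEs get time to first Grade 3 or 4 onset, and duration and dose intensity by arm would sit beside the AE tables. All of this stands. A reader might infer that every AE table other than the primary endpoint is exposed, or that the primary safety conclusion is at risk. The documents support neither.

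A second reply is that the whole-study tables are descriptive. That is right for the SAP text, but the protocol's overall Grade 3 or higher sensitivity comparison carries a difference and a CI. SAP Section 7 does not list it as dropped.

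A third is that the size is assumed. That also stands. A reader might take the 6 to 42 months as a difference between arms. It reflects when subjects enrol, which randomization should balance; a difference between arms would come from tolerability or progression, and no durations by arm are given. A gap of 5 points is also about a third of the 15-point half-width.

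A fourth is that the rate has its own bias. The front-loaded case confirms this, and it shapes the fix. It might also seem enough to divide events by the subject-months in SAP 5.6.1. Those stop at the last dose and keep counting after a first event, so they do not match the TEAE window.

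Finally, the table shells are in a separate document that was not available. An adjusted table there cannot be excluded, but the SAP text plans none.

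**Conclusion.** The gap is real and minor. Whole-study TEAE, SAE and CSE incidence, and the protocol's overall Grade 3 or higher comparison, mix event frequency with treatment time. They can mislead in either direction about the secondary endpoint of overall safety and tolerability. For CSEs the gap is narrower, because Grade 3 or 4 onset is timed, although the SAP gives no method or censoring rule for it.

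If median treatment differs by 12 versus 18 months, the false gap is about 3.5 to 6 points for constant hazards of 0.02 to 0.08 per month, and about 2 points in the front-loaded case. Under constant hazards, a true 20% reduction shrinks to less than 1 point. These figures rest on the assumed durations, accrual pattern and hazards, and on stopping being independent of the event. With similar durations in the two arms the problem largely disappears.

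**What to change.** In SAP 5.6.2, add by starting dose, for whole-study Grade 3 or higher TEAEs, SAEs and each CSE group:

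1. **Exposure-adjusted first-event rates**, with the rate difference and 95% CI. The denominator is time from first dose to the first event, 28 days after the last dose, or data cutoff, whichever is earliest. State that this is not the subject-months of SAP 5.6.1.
2. **Cumulative incidence of the first event at fixed times**, such as 24 weeks and 12 months. Choose the estimator in advance. Kaplan-Meier, censoring at the end of the 28-day window, assumes stopping is uninformative. Aalen-Johansen, with stopping as a competing event, does not, but its result still partly reflects treatment duration.

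Read the two together, since neither is free of assumptions. Keep the crude tables and the Week 24 primary safety endpoint unchanged. State in the SAP whether the protocol's overall Grade 3 or higher sensitivity comparison is retained and, if so, show these summaries beside it.

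The cost is a paragraph of SAP text and one set of tables from dates already collected. With 76 subjects per arm, intervals for individual CSE groups will be wide, so these summaries should be labelled supportive.
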